3.14 Medication

Preoperatively, the patient will not receive any kind of analgesic treatment. Additionally, 8 and 1 hour preoperatively, the patient will receive a fleet enema. Intraoperatively, besides the applied anesthetic technique, additional analgesia (paracetamol 1000mg I.V.) will be administered if deemed necessary. Perioperative antibiotic chemoprophylaxis will include the administration of a single dose of cefoxitin I.V. 2gr, and in case of allergy to cefoxitin, ciprofloxacin I.V. 400mg. With regard to the postoperative analgesic treatment, the patient will receive paracetamol 1000mg I.V every 6 hours, and if needed lornoxicam 8mg. In case of nausea or vomiting, granisetron 3mg/3ml I.V. will be administered. The patient will receive his systematic medication. Oral feeding will start upon absence of nausea and vomiting.

3.15 Research Group

Both the surgeon and the anesthesiologist who participate in the research group have years of experience in their field and have, therefore, completed the learning curve for the required operative and anesthesia techniques, respectively. The data collection and recording will be carried out by an independent, third party, researcher.

1.1 Description of the proposed project

The purpose of this study is to compare two techniques for treating hemorrhoids, the ligation and hemorrhoidopexy technique and the conventional ligation of hemorrhoidal arteries using ultrasound, in patients with non-complicated hemorrhoids.

2. Data Source

2.1 Trial

The study will be conducted in the Department of Surgery of the University Hospital of Larissa. Patient data will be recorded both in the patient charts and in an electronic database.

3. Analysis Objectives

3.1 Primary endpoint

The primary endpoint of the present study is the identification of difference in the symptoms remission rate, within one month postoperatively, between the ligation and hemorrhoidopexy technique and the conventional ligation of hemorrhoidal arteries using ultrasound, in patients with non-complicated hemorrhoids. If the symptoms are treated then it will be defined as=1 'YES' If the symptoms are not treated then it will be defined as=0 'NO'. The time frame will be 1 month postoperatively.

3.2 Secondary endpoints

The secondary endpoints of the present study are:

- Operative time. Measurement unit: minutes. Time Frame: Intraoperative period
- Postoperative mobilization time. Measurement unit: hours. Time Frame: Postoperative period up to hospital discharge. Maximum time frame 24 hours
- Postoperative pain level at 12 hours after surgery, quantified with the use of the VAS scale. Time Frame: 12 hours postoperatively
- Onset of oral feeding. Measurement unit: hours. Time Frame: Postoperative period up to hospital discharge. Maximum time frame 24 hours
- Difference in the rates of adverse effects during hospitalization:
 - Hypotension. Occurrence of postoperative hypotension. If such an episode occurs, then it will be defined as=1 'YES' If such an episode does not occur, then it will be defined as=0 'NO'. Time Frame: Postoperative period up to hospital discharge. Maximum time frame 24 hours
 - Nausea. Occurrence of postoperative nausea. If such an episode occurs, then it will be defined as=1 'YES' If such an episode does not occur, then it will be defined as=0 'NO'. Time Frame: Postoperative period up to hospital discharge. Maximum time frame 24 hours
 - Vomiting. Occurrence of postoperative vomiting. If such an episode occurs, then it will be defined as=1 'YES' If such an episode does not occur, then it will be defined as=0 'NO'. Time Frame: Postoperative period up to hospital discharge. Maximum time frame 24 hours
 - Headache. Occurrence of postoperative headache. If such an episode occurs, then it will be defined as=1 'YES' If such an episode does not occur, then it will be defined as=0 'NO'. Time Frame: Postoperative period up to hospital discharge. Maximum time frame 24 hours
 - Urinary retention. Occurrence of postoperative urinary retention. If such an episode occurs, then it will be defined as=1 'YES' If such an episode does not occur, then it will be defined

- as=0 'NO'. Time Frame: Postoperative period up to hospital discharge. Maximum time frame 24 hours
- Bleeding at the operative site. Occurrence of postoperative bleeding at the operative site. If such an episode occurs, then it will be defined as=1 'YES' If such an episode does not occur, then it will be defined as=0 'NO'. Time Frame: Postoperative period up to hospital discharge. Maximum time frame 24 hours
- Postoperative time that the patient can be safely discharged. Measurement unit: hours. Time Frame: Postoperative period up to hospital discharge. Maximum time frame 48 hours
- Complications occurring at 7 days postoperatively:
 - Pain on the basis of the VAS scale. Postoperative pain level at 7 days after surgery, quantified with the use of the VAS scale. Time Frame: 7 days postoperatively
 - Oedema at the operative site. Occurrence of postoperative oedema at the operative site. If such an episode occurs, then it will be defined as=1 'YES' If such an episode does not occur, then it will be defined as=0 'NO'. Time Frame: 7 days postoperatively
 - Hematoma at the operative site. Occurrence of postoperative hematoma at the operative site. If such an episode occurs, then it will be defined as=1 'YES' If such an episode does not occur, then it will be defined as=0 'NO'. Time Frame: 7 days postoperatively
 - Infection at the operative site. Occurrence of postoperative infection at the operative site. If such an episode occurs, then it will be defined as=1 'YES' If such an episode does not occur, then it will be defined as=0 'NO'. Time Frame: 7 days postoperatively
 - Stenosis at the operative site. Occurrence of postoperative stenosis at the operative site. If such an episode occurs, then it will be defined as=1 'YES' If such an episode does not occur, then it will be defined as=0 'NO'. Time Frame: 7 days postoperatively
- Postoperative return to work time. Measurement unit: days. Time Frame: Postoperative period up to 1 month
- Complications occurring at 1 year postoperatively:
 - Pruritus. Occurrence of postoperative pruritus at the operative site. If such an episode occurs, then it will be defined as=1 'YES' If such an episode does not occur, then it will be defined as=0 'NO'. Time Frame: 1 year postoperatively
 - Mucosal proptosis. Occurrence of postoperative mucosal proptosis at the operative site. If such an episode occurs, then it will be defined as=1 'YES' If such an episode does not occur, then it will be defined as=0 'NO'. Time Frame: 1 year postoperatively
 - Perianal nodules. Occurrence of postoperative perianal nodules. If such an episode occurs, then it will be defined as=1 'YES' If such an episode does not occur, then it will be defined as=0 'NO'. Time Frame: 1 year postoperatively
 - Constipation. Occurrence of postoperative constipation. If such an episode occurs, then it will be defined as=1 'YES' If such an episode does not occur, then it will be defined as=0 'NO'. Time Frame: 1 year postoperatively
 - Tenesmus. Occurrence of tenesmus. If such an episode occurs, then it will be defined as=1 'YES' If such an episode does not occur, then it will be defined as=0 'NO'. Time Frame: 1 year postoperatively.
 - Reoperation. Occurrence of reoperation. If the patient is reoperated, then it will be defined as=1 'YES' If the patient is not reoperated, then it will be defined as=0 'NO'. Time Frame: 1 year postoperatively
- Disease recurrence rate at 1 year postoperatively. Disease recurrence rate If such an episode occurs, then it will be defined as=1 'YES' If such an episode does not occur, then it will be defined as=0 'NO'. Time Frame: 1 year postoperatively
- Satisfaction level at 1 year postoperatively. Satisfaction level measured at a 0-10 scale. Time Frame: 1 year postoperatively
- Difference in the quality of life of the patient, at 1 month and 1 year postoperatively, compared to the respective preoperative measurements, based on the SF-36 questionnaire, weighted for the Greek. Time Frame: Preoperatively, 1 month postoperatively and 1 year postoperatively.

4. Analysis Set

4.1 Sample

The sample will consist of male and female patients aged 18 to 80 years, with an American Society of Anesthesiologists (ASA) score of I and II.

4.2 Diseases

Patients with Grade \leq III hemorrhoids, according to Goligher's classification, will be included.

4.3 Exclusion Criteria

The exclusion criteria include:

- Acute perianal diseases, such as perianal abscesses, complicated hemorrhoids (e.g., thrombosis) and acute anal fissure
- Malignant perianal disorders
- Patient age \geq 80 years
- ASA score \geq III
- Presence of inflammatory bowel disease
- History of a previous rectoanal operation
- Presence of a clinically significant cardiovascular, respiratory, renal, hepatic or metabolic disorder. Furthermore, diseases, such as obesity, psychiatric disorders or gastrointestinal disorders constitute exclusion criteria.

4.4 1st Arm

The patient will be placed in the Lloyd-Davies position and having provided a sterile field, using a 10% povidone iodine solution, rectal dilatation will be performed with a 10% xylocaine gel, thus allowing the entrance of the proctoscope (THD America). The proctoscope will be combined with a Doppler sensor in order to detect the hemorrhoidal arteries and, also, a light source. Furthermore, a casing at the distal end of the apparatus that allows the proper placement and rotation of the needle-holder and a special window above the sensor and, thus, enables the placement of the ligations at the correct height and depth, through the capturing of the mucosa and the submucosa and the prevention of the perforation of the rectal wall. After the hemorrhoidal artery location, through the use of the ultrasound, Z ligations will be placed, using an absorbable polyglycolic acid suture (2-0, 5/8 inch needle). The proper artery ligation will be confirmed by the absence of the Doppler signal. In the presence of residual hemorrhoidal tissue, the upper part of the proctoscope will be removed and hemorrhoidopexy will be performed, by applying a continuous suture from the hemorrhoidal stem and peripherally. During hemorrhoidopexy, only the mucosa and the submucosa of the hemorrhoidal nodules, above the dental line, will be captured. At the end of the procedure, a hemostatic gauze will be placed in the surgical field. Prior to operation, the patients will be submitted to spinal anesthesia. Using an atraumatic 25 Gauge (G) needle, a levobupivacaine 5mg/ml and fentanyl 25mg solution, will be administered at the height of lumbar (L)2-L3 or L3-L4.

4.5 2nd Arm

In the experimental arm, the patient will be placed in the Lloyd-Davies position and having provided a sterile field, using a 10% povidone iodine solution, rectal dilatation will be performed with a 10% xylocaine gel, thus allowing the entrance of a conventional proctoscope, with an attached light source. After the identification of the hemorrhoidal nodules (3rd, 7th, 11th hour), their ligation, using an absorbable polyglycolic acid suture (2-0, 5/8 inch needle), will be performed. The location of the hemorrhoidal artery will be confirmed, through palpation, with the use of the index finger. Initially, a fixative suture will be placed in the hemorrhoidal nodule and then, using a continuous suture from the hemorrhoidal stem and peripherally, hemorrhoidopexy, will be performed. During hemorrhoidopexy, only the mucosa and the submucosa of the hemorrhoidal nodules, above the dental line, will be captured. At the end of the procedure, a hemostatic gauze will be placed in the surgical field. Prior to operation, the

patients will be submitted to pudendal nerve block. Using an atraumatic 25 Gauge (G) needle, a 20ml lidocaine solution (diluted with saline in a 1:1 rate) will be administered bilaterally, medially to the ischial tuberosity. Ten minutes before the operation, the patient will receive 1-2.5mg midazolam and 0.1-0.2 mg fentanyl.

4.6 Covariates

The following data will be considered as covariates

- Demographics (Gender, Age, Weight, Height, ASA)
- Symptoms (Proptosis, Bleeding, Pruritus, Pain)
- Hemorrhoid Grade

5. Statistical Methodology

5.1 Sample Size calculation

The calculation of the sample size is based on the primary endpoint. According to the literature, the rate of the remission rate of symptoms, of patients who were submitted to hemorrhoidal artery ligation using ultrasound is 72.5%, while the respective rate of the ligation and hemorrhoidopexy technique is 90%. Therefore for a non-inferiority trial, with $\alpha= 2,5\%$, $\beta= 80\%$ and a non inferiority limit of 10% , the calculated sample for each group is 30 patients. Totally, the required number of patients is 60.

5.2 Handling of Missing Values

Missing values will be addressed using the multiple imputation method. Acceptable levels of missing values will be <10%.

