3.13 Follow up

One week after the operation, the patient will be summoned to reply for any postoperative complications, the return to work time, and the current pain level. One month postoperatively, the patient will be asked about the remission of the symptoms. One year after the operation, the patient will be examined for disease recurrence and will be asked about the overall satisfaction regarding the operation.

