5.3 Statistical Procedures

The statistical estimations of this study will be based on a per protocol analysis. Prior to any computation, all data will be submitted to a Shapiro-Wilk normality test.

Continuous variables will be compared on the basis of an independent samples t-test, whereas for categorical variables, the Pearson chi-square test will be applied.

The effect of the various patient characteristics on the primary and secondary endpoint will be evaluated by a regression analysis. More specifically, a multiple linear and a logistic regression will be used for continuous and categorical variables, respectively.

Regression analysis will be applied to all distinct endpoints. The validity of the linear regression model will be confirmed by the assessment of the following assumptions:

- Independence of observations, assessed by the Durbin-Watson test
- Linear relationship between the dependent variable and each of the independent variables and between the dependent variable and all the independent variables, collectively.
- Homoscedasticity of the data
- Multicollinearity of the data
- Absence of significant outliers, high leverage points or highly influential points
- Normal distribution of the residuals

A Forward model will be introduced in our multiple linear regression analysis. The proportion of variance explained by our model will be represented by R square. The statistical significance of our model will be evaluated by the F-test. The effect of each independent variable on the dependent outcome will be provided by the respective coefficient and the 95%CI.

Similarly, a Forward model will be applied in our logistic regression analysis. The following assumption will be tested:

- Independence of observations and mutual exclusive and exhaustive categories
- Linear relationship between any continuous independent variable and the logit transformation of the dependent variable

The explained variance will be presented by the Cox & Snell R square and Nagelkerke R square test. The percentage of the correctly classified observations will be also estimated. The statistical significance of each variable will be calculated by the Wald test. The odds ratios of each variable will be also estimated, alongside the respective 95%CI.

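### Missing 1-month remission is handled by multiple imputation alone, with no sensitivity analysis; at 30 per arm, missingness within the SAP's tolerance can cost some results their non-inferiority.

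*SAP*

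**What the plan says.** The primary endpoint is a yes/no record of symptom remission at one month (Protocol 3.6, SAP 3.1). It comes from one contact: "One month postoperatively, the patient will be asked about the remission of the symptoms" (Protocol 3.13). A patient who is not reached has no primary outcome.

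SAP 5.2 has two sentences: "Missing values will be addressed using the multiple imputation method. Acceptable levels of missing values will be <10" per cent. It gives no imputation model, missingness assumption, number of imputations or pooling rule. It does not say whether the limit applies overall, per arm or per variable, or what follows if it is exceeded.

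SAP 5.1 frames the trial as non-inferiority with "a non inferiority limit of 10" per cent and 30 patients per group, with no stated allowance for dropout. SAP 5.3 makes the analysis per protocol and says that "for categorical variables, the Pearson chi-square test will be applied". It also plans logistic regression with odds ratios. Neither document contains a complete-case, worst-case, tipping-point or other sensitivity analysis for missing outcomes.

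**The concern.** Standard multiple imputation assumes that patients who do not answer remit like comparable patients who do. The data cannot check that. Non-responders may include more failures (for example, patients who sought care elsewhere) or fewer. In a non-inferiority trial, filling in non-responders near their arm's average can mask failures in the experimental arm, which favours the conclusion sought.

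The trial is small: one patient in an arm of 30 moves that arm's rate by 3.3 points, against a margin of 10. A few missing answers could therefore matter, and the plan has no step that would show whether they do. Nor does it define the pooled quantity to compare with the margin. A chi-square test addresses equality, and an odds ratio is not on the scale of a margin in percentage points.

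**Working it through.** **Inputs from SAP 5.1.** Control remission 72.5% ("submitted to hemorrhoidal artery ligation using ultrasound is 72.5" per cent), experimental 90%, margin 10, alpha 2.5%, 30 per group.

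**Assumptions.** Alpha is one-sided, the figure printed as beta is power, and the margin is an absolute difference (experimental minus control). The plan names no confidence interval, so I use the Newcombe two-sided 95% interval: non-inferior if the lower limit lies above −10 points. The result on observed cases stands in for the imputed result when missingness carries no information. The 2 + 2 split of missing answers is mine.

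**The plan's own figure.** n = (1.960 + 0.842)² × (0.725 × 0.275 + 0.90 × 0.10) / (0.175 + 0.10)² = 30.03 per group. The stated 30 reproduces.

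**What the tolerance admits.** Below 10% of 60 is at most 5 patients (8.3%). Applied per arm, it is at most 2 of 30 (6.7%).

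**Range left open.** With 2 missing per arm, the difference can move by 2/30 + 2/30 = 13.3 points from best to worst case. With 5 missing in total, it is 5/30 = 16.7 points. Both exceed 10.

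**Worked results.** The Newcombe lower limit is d − √[(p_E − l_E)² + (u_C − p_C)²], where l_E is the Wilson lower limit of the experimental rate and u_C the Wilson upper limit of the control rate.

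- 24/28 v 20/28: 14.3 − √[(85.7 − 68.5)² + (84.7 − 71.4)²] = −7.5. Passes.
- 24/30 v 20/28 (only the two missing experimental patients counted as failed): 8.6 − √[(80.0 − 62.7)² + (84.7 − 71.4)²] = −13.3. Lost.

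| Observed | Lower limit, observed | Missing experimental failed, control as observed | Missing experimental failed, missing control remitted |
|---|---|---|---|
| 24/28 v 20/28 | −7.5 | −13.3 | −14.7 |
| 25/28 v 20/28 | −3.3 | −9.6 | −11.0 |
| 26/28 v 20/28 | +1.0 | −5.9 | −7.2 |

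The first result is lost under both scenarios, the second only at the extreme bound, the third under neither.

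**How often.** I enumerated all outcomes with 28 evaluable per arm, using binomial probabilities at 90% and 72.5%. On observed data 75.8% of trials pass. The share of those passes that is lost:

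| Assumption about the 2 + 2 missing patients | Share lost |
|---|---|
| All failed, both arms | 8.5% |
| Experimental failed, control at its observed rate | 30.9% |
| Experimental failed, control remitted (extreme bound) | 41.8% |

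The interval method changes little: with Wald limits 79.8% pass, and the extreme bound removes 39.5% of those.

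**The case against.** The strongest objection is that the large figures need opposite behaviour in the two arms. If failures are simply less likely to answer, the same should hold in both arms, and then only 8.5% of passes are lost. Protocol 3.10 plans to blind the patient and the postoperative recorder to technique, which argues against arm-specific missingness, although the anaesthesia differs by arm (Protocol 3.4 and 3.5). This stands: 41.8% is a bound, not a forecast.

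A reader might infer four stronger things that the documents do not support.

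- That tolerating nearly 10% missing uses up the 10-point margin. A share of patients and a risk difference are different quantities, and the matching tens are a coincidence. The relevant comparison is the 13.3 to 16.7 point range.
- That tolerated missingness will reverse the trial's result. It can reverse some results under stated assumptions; 26/28 v 20/28 survives the extreme bound.
- That the plan can produce no single answer after imputation. Methods for pooling chi-square statistics exist. The SAP names none, and a pooled chi-square would still test equality rather than the margin.
- That the conclusion will rest on imputed answers. The SAP does not say whether patients without a 1-month answer stay in the per-protocol set. If they are excluded, nothing is imputed for them, but the result then depends on an equally untested assumption that they resemble those who answered.

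**Conclusion.** The concern holds as a gap in specification that can affect the conclusion. The SAP relies on one untestable assumption for a primary outcome collected at a single contact, declares a level of missingness acceptable, and plans nothing to show whether the conclusion depends on it. With 2 missing per arm at the planning rates, between 8.5% and 41.8% of trials that pass on observed data would lose non-inferiority, depending on what is assumed about the missing patients. These shares rest on the 2 + 2 split, an absolute margin and the Newcombe interval. They do not show that the result would be wrong, or that the extreme bound is likely. This should be corrected before the data are analysed, so that the assumption is not chosen with the results in view.

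**What to change.** In SAP 5.2:

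1. Keep patients with a missing 1-month answer in the primary analysis set. Impute within arm, pool the risk difference and its standard error by Rubin's rules, and compare the lower 95% limit with −10 points.
2. Pre-specify a two-way tipping-point analysis that varies imputed remission in both arms, up to the bound at which missing experimental patients did not remit and missing control patients did. Report where non-inferiority is lost. Varying the experimental arm alone is not enough: 25/28 v 20/28 survives that (−9.6) but not the joint bound (−11.0).
3. Replace the statement that under 10% missing is acceptable with a commitment to report the non-inferiority conclusion together with its tipping point.

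The cost is SAP wording and a little extra analysis, with no added patients or visits. The downside is that the claim may have to be softened if several answers are missing.

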5.3 Statistical Procedures

The statistical estimations of this study will be based on a per protocol analysis. Prior to any computation, all data will be submitted to a Shapiro-Wilk normality test.

Continuous variables will be compared on the basis of an independent samples t-test, whereas for categorical variables, the Pearson chi-square test will be applied.

The effect of the various patient characteristics on the primary and secondary endpoint will be evaluated by a regression analysis. More specifically, a multiple linear and a logistic regression will be used for continuous and categorical variables, respectively.

Regression analysis will be applied to all distinct endpoints. The validity of the linear regression model will be confirmed by the assessment of the following assumptions:

- Independence of observations, assessed by the Durbin-Watson test
- Linear relationship between the dependent variable and each of the independent variables and between the dependent variable and all the independent variables, collectively.
- Homoscedasticity of the data
- Multicollinearity of the data
- Absence of significant outliers, high leverage points or highly influential points
- Normal distribution of the residuals

A Forward model will be introduced in our multiple linear regression analysis. The proportion of variance explained by our model will be represented by R square. The statistical significance of our model will be evaluated by the F-test. The effect of each independent variable on the dependent outcome will be provided by the respective coefficient and the 95%CI.

Similarly, a Forward model will be applied in our logistic regression analysis. The following assumption will be tested:

- Independence of observations and mutual exclusive and exhaustive categories
- Linear relationship between any continuous independent variable and the logit transformation of the dependent variable

The explained variance will be presented by the Cox & Snell R square and Nagelkerke R square test. The percentage of the correctly classified observations will be also estimated. The statistical significance of each variable will be calculated by the Wald test. The odds ratios of each variable will be also estimated, alongside the respective 95%CI.

The variations between the different time endpoints SF-36 measurements will be evaluated on the basis of a repeated measures ANOVA model. Violation of the sphericity assumption will be determined by the Mauchly's test of Sphericity. In case of significant results, a Greenhouse-Geisser correction will be applied. Post-hoc comparisons will be performed with the introduction of Bonferroni corrections. The effect of the allocation group on the measured group will be quantified by the use of the F-test.

Continuous data will be reported as Mean (Standard Deviation), while categorical data will be reported as N (Percentage). Statistical significance will be considered at the level of p value < 0.05. All analyses will be performed in the IBM SPSS Statistics v23 software

4.LITERATURE

2. Chan A-W, Tetzlaff JM, Altman DG, et al. SPIRIT 2013 statement: defining standard protocol items for clinical trials. *Ann Intern Med* 2013;158:200–7.
3. Henderson AR. Testing experimental data for univariate normality. *Clin Chim Acta* 2006;366:112–129.

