3.9 Randomization

The randomization of the patients, between the two groups, will be performed using a software and a 1: 1 allocation ratio will be performed. Furthermore, an opaque envelope, which will contain the allocation group for the specific patient, will be opened preoperatively upon the entry of the patient into the surgical room, thus determining which technique will be applied.

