3.10 Blinding

Blinding will exist at the level of the patient and the investigator who will record the data postoperatively, regarding the surgical technique applied. There will be no blinding at the level of the surgeon and the anesthesiologist.

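### Per-protocol is the only analysis population in the plan, it is not defined, and no analysis of all randomised patients by allocated arm is planned

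*SAP*

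**What the plan says.** SAP 5.3 (Statistical Procedures) sets the population in one sentence: "The statistical estimations of this study will be based on a per protocol analysis". The sentence is not limited to the primary endpoint, so it also covers the secondary endpoints of SAP 3.2. There are 26 of these if SF-36 is counted once. They are compared by t-test, chi-square, regression or repeated-measures ANOVA, under the rule "Statistical significance will be considered at the level of p value < 0.05".

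The SAP has a section headed "4. Analysis Set". Its first entry begins "The sample will consist of male and female patients aged 18 to 80 years". The rest covers hemorrhoid grade, exclusion criteria, the two operative techniques and a covariate list. Nothing there says which deviations remove a patient, who decides, or when.

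Three other passages bear on the point:

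- Protocol 3.9: the allocation envelope "will be opened preoperatively upon the entry of the patient into the surgical room".
- Protocol 3.10: "There will be no blinding at the level of the surgeon and the anesthesiologist". The patient and the postoperative recorder are blinded, and Protocol 3.15 adds "The data collection and recording will be carried out by an independent, third party, researcher".
- SAP 5.2: "Missing values will be addressed using the multiple imputation method". It does not say to which patients this applies.

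**The concern.** A per-protocol set is chosen after randomisation. If the reasons for leaving it out are related both to the arm and to how the operation went, the two groups compared are no longer the two groups randomised. Non-inferiority trials accept a per-protocol analysis because an intention-to-treat analysis can blur a real difference. That is a reason to run both and compare them, not to drop one. It is also no reason to use per-protocol for pain, complications, return to work or recurrence, which are tested for a difference.

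The missing definition leaves practical questions open:

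- **Hemorrhoidopexy in the 1st arm.** It is conditional on residual tissue. Without a rule, an analyst could call it adherence or crossover.
- **Age exactly 80.** SAP 4.1 includes it and SAP 4.3 excludes it, so even a set built on eligibility is ambiguous. The two passages must be reconciled.
- **No 1-month outcome.** The patient might be imputed or excluded.

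At stake is whether a reader can tell if the primary conclusion, or any secondary one, depends on who was left out.

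**Working it through.** **Inputs from the documents (SAP 5.1).** Remission 72.5% control and 90% experimental; margin 10 points, read as absolute; alpha 2.5%, read as one-sided; power 80% (printed as beta); 30 per arm.

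**Inputs assumed.** The documents give no deviation rate, so 0 to 3 exclusions per arm are used. The SAP names no interval for the risk difference, so the Newcombe two-sided 95% interval is used. The counts 24/30 and 22/30 are illustrative.

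**1. The plan's own figure.** With unpooled variance,

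n = [0.725×0.275 + 0.90×0.10] × (1.960 + 0.842)² / (0.175 + 0.10)² = 30.03 per arm.

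The stated 30 is reproduced (31 if rounded up). Power = Φ(0.275/√(0.289375/n) − 1.960):

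- n = 30: Φ(2.800 − 1.960) = 80.0%
- n = 27: Φ(2.656 − 1.960) = 75.7%

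The sample size leaves no room for exclusions.

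**2. Selective exclusion (worst case).** Newcombe lower limit = d − √[(pE − lE)² + (uC − pC)²], where l and u are Wilson limits. For control 22/30, pC = 0.733 and uC = 0.858. For experimental 24/30, pE = 0.800 and lE = 0.627. So

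0.067 − √(0.173² + 0.125²) = −0.147.

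Now remove experimental-arm failures only:

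| Experimental | Control | Difference (points) | Lower limit (points) |
|---|---|---|---|
| 24/30 | 22/30 | 6.7 | -14.7 |
| 24/29 | 22/30 | 9.4 | -11.9 |
| 24/28 | 22/30 | 12.4 | -8.9 |
| 24/27 | 22/30 | 15.6 | -5.5 |

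Two exclusions out of 60 patients reverse the result against the -10 margin.

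**3. False non-inferiority claims.** Take true rates of 62.5% and 72.5%, exactly at the margin. Summing exact binomial probabilities over all outcomes with 30 per arm, the false-claim rate is 2.7% with no exclusions. It is 4.6%, 6.6% or 10.5% when up to one, two or three experimental failures may be removed selectively.

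**4. Exclusions unrelated to outcome.** Start again from 24/30 versus 22/30 and drop three at random from each arm (hypergeometric). The lower limit becomes worse than -14.7 with probability 75.3% and rises above -10 with probability 3.8%.

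**5. Power of the alternatives.** Exact calculation at 90% versus 72.5% with the Newcombe rule and three random exclusions per arm:

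| Rule | Power |
|---|---|
| Intention-to-treat alone (30 per arm) | 77.5% |
| Per-protocol alone (27 per arm, present plan) | 74.9% |
| Both sets must clear the margin | 72.3% |

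**The case against.** - **The planned test does not flip.** The SAP plans a Pearson chi-square, not an interval against the margin. On the counts above, p is about 0.54 for 24/30 versus 22/30 and about 0.14 for 24/27 versus 22/30, so neither is significant. This is true, and the reversal appears only once a margin test is added. It does not rescue the plan, because a non-significant difference cannot establish non-inferiority within 10 points.
- **The worst case needs hindsight.** A departure in the operating room happens before the 1-month outcome is known, so it cannot pick out exactly the future failures. This stands as a limit on the size of the effect. A difficult operation may still predict failure imperfectly, and nothing in the plan stops exclusions being settled after outcomes are known.
- **Random exclusions usually hurt the claim.** This stands. Per-protocol is not shown to favour non-inferiority in general.
- **Exposure may be small.** Treatment is a single procedure, allocation is opened late, the primary endpoint is at one month, and missing values are imputed. If nobody deviates, the two sets coincide. That is possible, but conversion, a change of anaesthesia and loss to follow-up remain open. Imputation fills in values; it does not restore excluded patients.
- **Recording is blinded and independent.** This protects how outcomes are recorded, not who enters the analysis.
- **SAP section 4 is an implicit definition.** It can be read as eligible patients treated as described. It still lists no deviations, no decision-maker and no timing.

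**Conclusion.** The concern holds, with high confidence, and must be fixed. It rests on the text: one population, no definition, and no analysis of all randomised patients as allocated, for the primary endpoint or for the secondary endpoints tested for a difference. A set defined after outcomes have been seen by arm would not be credible.

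The calculations show sensitivity, not expected bias. They depend on the assumed counts, the assumed 0 to 3 exclusions per arm and the added Newcombe margin test. Under those assumptions two selective exclusions are enough to change the primary conclusion, while outcome-neutral exclusions would more often make it harder to reach.

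**What to change.** In SAP section 4, define two sets:

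- **Intention-to-treat:** all randomised patients, analysed in the allocated arm.
- **Per-protocol:** a listed set of excluding deviations, applied by someone unaware of outcomes and before outcomes are compared by arm. Hemorrhoidopexy for residual tissue in the 1st arm is already part of the described procedure and should not count as a deviation.

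In SAP 5.3, name the two-sided 95% interval for the risk difference (Newcombe, for example) and report the primary endpoint in both sets. Claim non-inferiority only if both lower limits lie above -10 points. The both-sets rule is a conservative convention; the essential step is to define and report both. Make intention-to-treat the main set for secondary endpoints, with per-protocol as a sensitivity analysis. Report exclusions by arm with reasons, and say in SAP 5.2 which patients are imputed.

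The cost is SAP wording and a second run on data already collected. With three random exclusions per arm, the both-sets rule lowers exact power from 74.9% under the present plan to 72.3%, about 2.5 points before rounding. Intention-to-treat alone would have 77.5%.
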